Although the efficacy of LCPT has been shown for use in kidney transplant patients, there is still a need for observing medication adherence with regards to the once a day treatment. This study will look at medical adherence with regards to its outcomes in kidney transplant recipients in order to better understand how a once a day regimen of tacrolimus may be beneficial to patients. Drugs work in a dose and time dependent manner and more emphasis is being put on electronic monitoring of medication adherence (Vrijens & Heidbuchel, 2015). This study may utilize Medisafe Medication Manager to accurately track adherence of the study medication.

C Study Objectives

C1 Primary Aim

Aim 1: To determine whether an immunosuppressive maintenance regimen of Envarsus/azathioprine regimen compared to a tacrolimus/ mycophenolic acid regimen is associated with better compliance and tolerability. This may be examined by a survey to the patients at 3 and 12 months. In addition, for patients with smart phone, we may examine their adherence through “Pill Manager by Medisafe” app. This app tracks missed/taken doses.

C2 Secondary Aim

Aim 2: To determine whether an Envarsus/azathioprine regimen compared to a tacrolimus/ mycophenolic acid regimen is associated with a lower composite endpoint of biopsy proven acute rejection, graft loss, death and lost to follow up at 12 months after kidney transplantation. Biopsy will be performed if clinically indicated

C3 Rationale for the Selection of Outcome Measures

Acute Rejection:

We do not perform a protocol biopsy in our center, however, we have a low threshold to do a biopsy if there is an increased creatinine, proteinuria (urine protein/ creatinine > 1 gram), or de novo DSA with high level MFI. The decision of the biopsy will be based on

the decision of the clinician. Acute rejection can lead to failure and loss of the grafted kidney and is an important endpoint in many kidney transplant studies.

Graft Failure:

Graft failure will be defined by the return to hemodialysis, re-transplantation, or patient death. Death-censored graft failure will be defined as the return to hemodialysis or re-transplantation. Graft failure was chosen due to its importance in patient outcome.

Adherence:

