AZA starting dose will be between 1.5 - 2 mg/kg daily, rounded to nearest 50 mg. MPA (Myfortic) will be started 720 mg po BID and will be decreased to 360 mg BID when the Tac-IR trough level is therapeutic (according to the current goals in the center's protocol).

Immunosuppression administered at the study site will be recorded in the medical record and on a study drug diary. Immunosuppression doses administered at home will be recorded only on the study drug diary.

Tacrolimus trough target levels in both arms will be 7 to 10 ng/dL in the first month, then 5 to 7 afterward. Higher or lower tacrolimus trough level goals will be adjusted during the study due to clinical reasons such as history of rejection or infections post transplant at the discretion of the transplant nephrologists.

CBC, BMP or renal panel (including creatinine, eGFR) Tac trough levels will be checked once a week for the first four months then once every other weeks till the end of the study.

Known medication side effects: There are known common side effects to each medication. Tacrolimus has known side effects of tremors, sleep difficulty irregardless of its therapeutic range. Other side effects such as electrolyte abnormality in hyperkalemia, hypertension, and increased creatinine (if above therapeutic range) are known side effects as well. Both azathioprine and mycophenolate mofetil/mycophenoic acid have side effect of leukopenia and anemia. Azathioprine can also have elevated liver enzymes as a rarer side effect. Mycophenolate mofetil/mycophenoic acid have a known side effect of gastrointestinal upset or diarrhea.

E Study Design

E1 Overview or Design Summary

This will be an open label pilot study in which patients will be categorized into once a day regimen (Envarsus and azathioprine) or twice a day regimen (immediate release tacrolimus and mycophenoic acid) after kidney transplantation. We will enroll 50 patients in each arm after transplantation. Patients will be seen as per our usual follow up schedule until month 12 (+/- 29 days) from the time of transplant (time from transplant: week 2-4, week 5-8, week 9-12, month 6, month 9 and month 12 all +/- 2 weeks). Completion of the trial will be within 3 years. Outcomes can be reported/published by the end of the third year.

E2 Subject Selection and Withdrawal

2.a Inclusion Criteria

- Age \geq 18 years
- kidney transplant recipient
- Thymoglobulin induction

2. b Exclusion Criteria

- Non-renal organ transplant

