- Combined organ transplant
-
- Discharge to an acute-care facility after transplant

2.a Ethical Considerations

All patients will be given actual immunosuppressive medications (not placebo) in combinations that we have used in other patients at our transplant center. The only difference is one group will have medications dosed once a day and the other group will be on medications that are dosed twice a day, as per the medication administration recommendations.

2.b Subject Recruitment Plans and Consent Process

We will enroll 50 patients in each arm at the time of transplantation. Accounting for dropout of 20% from the study, we plan to possibly need to consent 120 patients total to obtain the 100 patient total number who complete the study. Subjects that meet the study inclusion criteria and without exclusion criteria will be approached in person prior to discharge from the hospital. The consenting process will be done in person by a study team member. Patients will be given the opportunity to look over the consent form and ask questions. A copy of the signed consent form will be provided to the patient once signed. Patients will be seen as part of the study until month 12 (+/- 29 days) from the time of transplant.

2.c Randomization Method and Blinding

We will approach patients after transplantation, prior to discharge. If patients are eligible to receive either tacrolimus or Envarsus, then we will approach them for participation in the study. If the patient consents to the study, we will enroll patients until we reach 50 patients in each arm of the study. There is no randomization done. Because this is an open label study, blinding is not conducted.

2.d Risks and Benefits

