Patients will all be on an immunosuppression regimen that we have used for patients we currently manage at our center. We have used both types of regimen on our patients, depending on tolerability and if there are any side effects that patients need switching to different regimens. Each regimen has been well tolerated by other patients. The major risks are with the side effects of the medications (see “11. d iii Expectedness of side effects to medications and adverse events”). It is expected that patients will adhere to the prescribed medication regimen, though some patients may not, especially to the twice daily regimen. We will attempt to mitigate this by asking patients use the pill reminder application. Patients are counselled on the importance of medication adherence for transplantation due to risk of rejection if they are not adherent. The benefits to patients include for those on the once daily regimen, less overall pill burden. Otherwise there is no additional benefit to patients.

2.e Early Withdrawal of Subjects

In the unlikely event that a patient is removed from study for unacceptable adverse event(s), such patient will be followed until resolution or stabilization of the adverse event. Participants that wish to withdraw from the study, or meet other early withdrawal material will have an End of Study/Early Termination Visit form filed. When possible or necessary, additional information about the patient (i.e. AEs, reason for withdrawal, etc.) will be gathered upon withdrawal of the study.

2.f When and How to Withdraw Subjects

Patients will be seen until month 12 (+/- 29 days) from the time of transplant. At the end of this period, an End of Study/Early Termination Visit form will be filed. Subjects will be notified of their completion or withdrawal from the study and briefed appropriately on what final steps should be taken.

2.g Data Collection and Follow-up for Withdrawn Subjects

Once withdrawn from the study, for safety reasons, patients will be followed via their labs and regular clinic visits for 12 months post withdrawal.

E3 Study Drug

3.a Description

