We will approach patients after transplantation. Patients will either receive tacrolimus or Envarsus based on insurance coverage. We will approach patients for the study after we have determined the form of calcineurin inhibitor they will be taking. If the patient consents to the study, we will enroll patients until we reach 50 patients in each arm of the study. If needed, the antimetabolite may be transitioned to the once or twice daily dosed medication, prior to discharge so that they may receive the medications prior to their discharge from the hospital. Because this is an open label study, blinding is not conducted.

3.d Preparation and Administration of Study Drug

Study medications may be self-administered by the patient. When not on the study site, all medications will be ordered through patient's preferred pharmacy. Suggestion will be made to utilize only subspecialty pharmacies.

3.e Subject Compliance Monitoring

We may use "Pill Reminder by Medisafe" for recipients who have I-phone or android smart device. Installing the app will take place before discharge. Records from the smart phone will be emailed from the device at the clinic visit at months 3 and 12. We understand that not all patients may have a smart device/phone, and so we plan to also use a survey – BAASIS. The BAASIS survey may be distributed at months 3 and 12. Average variability in tacrolimus levels for the follow-up period preceding each of the surveys may be calculated and compared between the two groups. Pharmacies may be contacted to assess for timing between refills to ensure that patients have taken medication as scheduled.

3.f Prior and Concomitant Therapy

Patients will receive induction therapy with either anti-thymocyte globulin or basiliximab at the time of transplantation. Depending on patient's prior medical history, they may have had prior immunosuppression and may be on immunosuppression prior to their transplant. This will not interfere with the study protocol or eligibility except if they meet exclusion criteria.

3.g Packaging

Study drugs will be packaged according to standard procedures for the medication.

3.h Blinding of Study Drug

This is an open label pilot study. The patients and study members will not be blinded to the study drug.

3.i Receiving, Storage, Dispensing and Return

Study medications may be self-administered by the patient. Study medications may be administered at the study site or ordered through patient's preferred pharmacy.

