At each study visit, we will collect the data as described in the study table and in the protocol description. The PI or study staff will review the data on an ongoing basis and every quarter for accuracy and completeness. Adverse effects will be routinely reviewed and recorded at each visit. Additionally any adverse event reported to the transplant physician, transplant coordinator or study coordinator including emergency department evaluation and/or hospitalization will be reviewed and documented by the principal investigator. Adverse event reporting will be done per the study agreement.

The study team will meet quarterly to review outcomes and safety of patients enrolled in the study as well as AEs. SAEs will be reviewed per occurrence.

Data on adherence to the treatment protocol may be collected via surveys and on Pill Reminder by Medisafe (emailed to research staff) at months 3 and 12. Adherence will be reviewed quarterly by the PI and the study statistician.

10.b Medical Monitoring

i Investigator and research team only

Both arms will follow the standard protocol visits in our clinics and will be seen at week 2-4, week 5-8, week 9-12, month 6, 9, and 12 (all +/- 2 weeks). These visits will include a focused physician exam, evaluation of adverse events as defined by the Common Toxicity Criteria of the National Cancer Institute and assessment of the patient's Immunosuppression. Labs are followed as per the center standard protocol and will be performed at the patients' designated lab outpatient.

10.c Definitions of Adverse Events

Adverse event means any untoward medical occurrence associated with the use of a drug in humans, whether or not considered drug related.

Life-threatening adverse event or life-threatening suspected adverse reaction. An adverse event or suspected adverse reaction is considered "life-threatening" if, in the view of either the investigator or sponsor, its occurrence places the patient or subject at immediate risk of death. It does not include an adverse event or suspected adverse reaction that, had it occurred in a more severe form, might have caused death.

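### Aim 2 counts loss to follow-up as an efficacy event in arms formed by insurance coverage, so retention alone can create or hide a difference in the composite

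*Combined protocol and SAP*

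**What the plan says.** - **Outcome.** Section C2 (Secondary Aim) asks whether the once-daily arm shows a lower rate of this outcome: "composite endpoint of biopsy proven acute rejection, graft loss, death and lost to follow up at 12 months after kidney transplantation". The four components carry equal weight.
- **How arms arise.** E2 2.c states that there is no randomisation. E3 3.c says: "Patients will either receive tacrolimus or Envarsus based on insurance coverage". This is settled before patients are approached.
- **Planned dropout.** E2 2.b (Subject Recruitment Plans) reads "Accounting for dropout of 20% from the study" and expects to "need to consent 120 patients total to obtain the 100 patient total number who complete the study". The same section says "We will enroll 50 patients in each arm at the time of transplantation".
- **After withdrawal.** Under E2 2.g, for safety, "patients will be followed via their labs and regular clinic visits for 12 months post withdrawal". Section A3 says that follow-up is the usual clinic schedule, with no extra study visits.
- **Analysis.** G2 covers graft and recipient survival (Kaplan-Meier, log-rank, Cox) and adherence (logistic regression). It names no method for the composite and no handling of losses.
- **Month 12 timing.** E1 runs follow-up "until month 12 (+/- 29 days) from the time of transplant" and, in the same sentence, gives the month 12 visit 2 weeks either side. E2 2.b and 2.f repeat the wider window. F10 10.b gives the narrower one: "month 6, 9, and 12 (all +/- 2 weeks". The documents do not define loss to follow-up.

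**The concern.** Counting loss as failure can be defended when randomisation makes loss comparable between arms and loss is rare. Neither safeguard is assured here. Coverage determines the arm and, under J3, also pays for the study medication, so it could plausibly bear on who stays under observation. The study is open label as well.

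The Aim 2 claim is directional: a lower composite for the once-daily regimen. If retention differs between arms for reasons unrelated to the drugs, the composite can differ while rejection, graft loss and death are identical. Unequal loss can also offset a real clinical difference. Either result would carry into the further investigation that G1 says this pilot is meant to inform.

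**Working it through.** **The plan's own figure.** 100 × 1.20 = 120 reproduces the number to consent. If 20% of those consented drop out, the number needed is 100 / 0.80 = 125, and 120 consented would leave 120 × 0.80 = 96. Read the other way, 20 dropouts among 120 is 16.7%. Both 20% and 16.7% are used below.

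**Inputs.** L is the proportion lost. The plan states dropout, not loss, so treating the two as equal is an assumption, and smaller values are shown. c is the rate of rejection, graft loss or death among those not lost. The documents give no value, so a range is used.

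**Share of the composite that is loss.** The composite is L + (1 − L)c, and the share due to loss is L / [L + (1 − L)c].

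| L | c = 5% | c = 10% | c = 15% | c = 20% | c = 25% | Loss is the majority when c is below |
|---|---|---|---|---|---|---|
| 20% | 83% | 71% | 63% | 56% | 50% | 25% |
| 16.7% | 80% | 67% | 57% | 50% | 44% | 20% |
| 10% | 69% | 53% | 43% | 36% | 31% | 11% |
| 5% | 51% | 34% | 26% | 21% | 17% | 5.3% |

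The last column is L / (1 − L): 0.20 / 0.80 = 25%, and 0.10 / 0.90 = 11%.

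**A difference created by loss.** Assume c = 10% in both arms, 50 per arm, and a Pearson test at two-sided 0.05 (the plan names no test for the composite). Each row is an exact enumeration over the two binomial counts.

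| Loss, arm 1 vs arm 2 | Composite | Declared different |
|---|---|---|
| 20% vs 20% | 28.0% vs 28.0% | 5% |
| 18% vs 22% | 26.2% vs 29.8% | 7% |
| 15% vs 25% | 23.5% vs 32.5% | 17% |
| 10% vs 30% | 19.0% vs 37.0% | 53% |

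For example, 0.10 + 0.90 × 0.10 = 0.19 and 0.30 + 0.70 × 0.10 = 0.37. With 60 per arm (120 consented), a normal approximation gives about 19% and 60% for the last two rows. The labels can be swapped, so the result can favour either regimen.

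**A difference hidden by loss.** Suppose the clinical rates are 20% vs 10%.
- Equal 20% loss turns them into 0.20 + 0.80 × 0.20 = 36% and 0.20 + 0.80 × 0.10 = 28%. The 10-point difference becomes 8 points. Power with 60 per arm falls from about 33% to 15%.
- Loss of 15% vs 25% gives 0.15 + 0.85 × 0.20 = 32.0% and 0.25 + 0.75 × 0.10 = 32.5%. The clinical difference disappears.

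**The case against.** The strongest reply is that dropout is not loss. Leaving the study need not mean leaving the clinic: visits and laboratory tests are usual care, and E2 2.g keeps withdrawn patients under observation for a year. If that works, few patients are truly lost and the 20% row does not apply. This stands. A reader might infer that the composite mostly measures retention, but the documents do not support that. It would need all dropout to be loss and a low clinical event rate, and the plan gives neither. What remains is that no rule says a withdrawn patient with known status is not counted as lost.

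Second, 10% vs 30% loss is a chosen extreme. Nothing in the documents says that insurance affects retention, by how much, or in which direction. This also stands, and it is why the benign rows are shown beside the extreme one.

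Third, a reader might infer that the two month 12 windows decide who is lost. They are visit windows, and no section links either one to loss. The conflict needs reconciling, but it is a separate, clerical matter.

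Fourth, if the 50 per arm are completers, that set holds no lost patients and the component would be empty. That shows the analysis set needs stating; it does not remove the difficulty.

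Finally, this is a secondary aim in a pilot. That limits the weight of the point, but the remedy is small.

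**Conclusion.** The point holds as a risk that the plan leaves open. Loss to follow-up has equal weight with clinical events, arms are set by coverage without randomisation, 20% dropout is planned, and no planned analysis separates the two. Loss can dominate the composite: it is the majority of events when the clinical rate is below 25% if all 20% dropout is loss, and below about 11% if loss is 10%. With identical clinical events at an assumed 10%, the chance of a declared difference runs from 5% (equal loss) through 7% and 17% to 53% at the extreme. The size depends on the actual loss by arm and the clinical event rate, neither of which the documents supply. Whether loss would favour or count against the once-daily arm cannot be told from the plan.

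**What to change.** 1. Keep the Aim 2 composite. Report beside it the clinical composite of rejection, graft loss and death, with loss by arm as its own line. Do not read a lower composite as better efficacy when the difference comes from loss.
2. Use the 2.g follow-up and usual-care records to establish 12-month status, and state that a withdrawn patient with known status is not counted as lost.
3. If patients who remain lost are censored at last contact, state that this assumes non-informative loss, which is open to doubt when coverage defines the arms. Add a sensitivity analysis, for example counting the lost as event-free. The existing composite already shows them all as events.
4. Name the method for the composite in G2, and state whether the analysis set is all enrolled patients or completers.
5. Separately, define loss to follow-up, and reconcile the 29-day and 2-week month 12 windows in E1, E2 2.b, E2 2.f and F10 10.b.

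The cost is some wording in the plan, one added analysis with its sensitivity check on data already collected, and a check of clinic records for withdrawn patients. The drawbacks are fewer events in the clinical composite, hence less precision, and reliance on the censoring assumption.

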We may use "Pill Reminder by Medisafe" for recipients who have an iPhone or Android smart device. Installing the app will take place before discharge. Records from the smart phone will be emailed from the device at the clinic visit at months 3 and 12.

A survey may be distributed at months 3 and 12. Other surveys may also be distributed to examine any possible side effects.

Average variability in tacrolimus levels for the follow-up period preceding each of the surveys may be calculated and compared between the two groups

Pharmacies may be contacted to assess for timing between refills to ensure that patients have taken medication as scheduled.

These methods were chosen due to their simplicity and usefulness in gaining information on patient adherence.

D Investigational Agent

D1 Clinical Data to Date

Twice-daily Tacrolimus is a standard for most kidney transplant recipients as part of a normal immunosuppression regimen (Budde et al., 2014; Rostaing et al., 2016).

Tacrolimus is effective in preventing acute rejection after kidney transplantation (Budde et al., 2014). Recently, an extended release version of tacrolimus has been produced for once a day administration (LCP-Tacrolimus tablets [LCPT], Veloxis Pharmaceuticals, Hørsholm, Denmark) (Bunnappadist et al., 2013). Multiple studies have shown LCPT to have a higher bioavailability, requiring lower doses to maintain the same trough levels as a twice a day regimen (Budde et al., 2014; Bunnappadist et al., 2013; Rostaing et al., 2016). A phase three, double blind randomized trial showed the LCPT treatment group to have fewer treatment failures compared to the twice a day regimen (Rostaing et al., 2016). These results were seen in black recipients, older recipients, and females, which are populations that are particularly high risk for rejection (Rostaing et al., 2016).

Adverse events and kidney function was similar between the LCPT and twice a day groups, showing comparable efficacy for the treatment (Rostaing et al., 2016).

D2 Dose Rationale and Risk/Benefits

Patients will be started on an antimetabolite in both arms (AZA or MPA) on post operation day 0 or 1 depending on the time they are able to take oral medication post surgery. Calcineurin inhibitors (Tac-IR or Tac-LCP) will be started on post operation day 1. Starting dose for Tac-IR is started at 0.1 mg/kg divided into BID. Starting dose for

Tac-LCP will be 0.08 mg/kg. These are starting doses per the center usual starting doses.

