Twice-daily Tacrolimus is a standard for most kidney transplant recipients as part of a normal immunosuppression regimen (Budde et al., 2014; Rostaing et al., 2016). Tacrolimus is effective in preventing acute rejection after kidney transplantation (Budde et al., 2014). Recently, an extended release version of tacrolimus has been produced for once a day administration (LCP-Tacrolimus tablets [LCPT], Veloxis Pharmaceuticals, Hørsholm, Denmark) (Bunnappadist et al., 2013). Multiple studies have shown LCPT to have a higher bioavailability, requiring lower doses to maintain the same trough levels as a twice a day regimen (Budde et al., 2014; Bunnappadist et al., 2013; Rostaing et al., 2016).

Azathioprine is a once a day medication that reduces purine synthesis through direct inhibition of the cell cycle. Similar kidney function and graft survival was found in long-term follow up studies comparing azathioprine to mycophenolate mofetil. In addition, unlike mammalian target of rapamycin inhibitors, azathioprine is not associated with nephrotoxicity or proteinuria.

3.b Treatment Regimen

Patients will be started on antimetabolite in both arms (AZA or MPA) on post operation day 0 or 1. Calcineurin inhibitors (Tac-IR or Tac-LCP) will be started on post operation day 1. Starting dose for Tac-IR will be 0.1 mg/kg divided into BID. Starting dose for Tac-LCP will be 0.08 mg/kg.

Immunosuppression administered at the study site will be recorded in the medical record and on a study drug diary. Immunosuppression doses administered at home will be recorded only on the study drug diary.

Tacrolimus trough target levels in both arms will be 7 to 10 ng/dL in the first month, then 5 to 7 afterward.

CBC, BMP or Renal panel (including creatinine, eGFR) Tac trough levels will be checked once a week for the first four months then once every other weeks as part of standard of care labs post transplant. These will be collected as data points during the study duration.

AZA starting dose will be 2 mg/kg, rounded to nearest 50 mg. MPA (Myfortic) will be started 720 mg po BID and will be decreased to 360 mg BID when the Tac-IR trough level is therapeutic (according to the current protocol).

3.c Method for Assigning Subjects to Treatment Groups

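### The tacrolimus trough target for both arms is printed in ng/dL, 100-fold below the same numbers in ng/mL: a minor unit error in an operative dosing target

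*Combined protocol and SAP*

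**What the plan says.** D2 (Dose Rationale and Risk/Benefits) and E3 3.b (Treatment Regimen) carry the same sentence: "Tacrolimus trough target levels in both arms will be 7 to 10 ng/dL in the first month, then 5 to 7 afterward". The second range has no unit of its own. No other section gives a unit for a tacrolimus level, and ng/mL appears nowhere.

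The surrounding text bears on how the target would be used:

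- **Starting doses** (E3 3.b): "Starting dose for Tac-IR will be 0.1 mg/kg divided into BID. Starting dose for Tac-LCP will be 0.08 mg/kg". D2 adds that these are the center's usual doses: "Tac-LCP will be 0.08 mg/kg. These are starting doses per the center usual starting doses".
- **Dose and trough** (D1): the once-daily product is described as "requiring lower doses to maintain the same trough levels as a twice a day regimen". This gives a direction but no predicted level.
- **Monitoring** (D2): "Tac trough levels will be checked once a week for the first four months", then every other week.
- **Mycophenolic acid step-down** (D2): the dose is halved "when the Tac-IR trough level is therapeutic (according to the current goals in the center's protocol"). E3 3.b repeats the step-down but refers only to the current protocol.
- **Discretion** (D2): "Higher or lower tacrolimus trough level goals will be adjusted during the study due to clinical reasons", at the transplant nephrologists' judgment. E3 3.b repeats the target without this clause.

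**The concern.** The target is the only numeric tacrolimus exposure goal in the protocol, and it stands in treatment text rather than background. The printed concentration is so low that the protocol's own starting doses would be expected to overshoot it by an order of magnitude or more. The unit and the dosing therefore do not fit together.

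Anyone who took the sentence literally would cut doses to reach the printed level. In kidney transplant recipients that means underexposure and a risk of rejection. The target is also the reference for frequent checks: weekly for four months (about 17) and every other week for eight months (about 17), or roughly 35 troughs per patient over the year.

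**Working it through.** **1. Unit conversion (no assumptions).** 1 dL = 100 mL, so x ng/dL = x/100 ng/mL.

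- First month: 7/100 = 0.07 and 10/100 = 0.10 ng/mL.
- Afterward, if the unit carries over: 5/100 = 0.05 and 7/100 = 0.07 ng/mL.

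The target is a stated value, not the result of a calculation in the protocol, so there is no figure to reproduce. The conversion shows the size of the discrepancy but not which unit was meant.

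**2. Comparison with the starting doses.** The protocol gives 0.1 mg/kg (Tac-IR) and 0.08 mg/kg (Tac-LCP), read here as daily totals. It gives no weight, clearance or average-to-trough ratio. I assume 50 to 100 kg, apparent clearance of 10 to 60 L/h, and an average level 1 to 2 times the trough.

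Predicted trough = daily dose / 24 h / apparent clearance / ratio

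| | Lowest (50 kg, 60 L/h, ratio 2) | Highest (100 kg, 10 L/h, ratio 1) |
|---|---|---|
| Tac-IR | 5,000,000 ng / 24 / 60,000 mL/h / 2 = 1.74 ng/mL | 10,000,000 / 24 / 10,000 / 1 = 41.7 ng/mL |
| Tac-LCP | 4,000,000 / 24 / 60,000 / 2 = 1.39 ng/mL | 8,000,000 / 24 / 10,000 / 1 = 33.3 ng/mL |

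Excess over the printed upper limit of 0.10 ng/mL:

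- Tac-IR: 1.74/0.10 = 17-fold to 41.7/0.10 = 417-fold.
- Tac-LCP: 1.39/0.10 = 14-fold to 33.3/0.10 = 333-fold.

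**3. A mid-case (70 kg, 30 L/h, ratio 1.5).** Tac-IR: 7,000,000 / 24 / 30,000 / 1.5 = 6.5 ng/mL. Tac-LCP: 5,600,000 / 24 / 30,000 / 1.5 = 5.2 ng/mL. Both are below 7, so the check shows compatibility with 7 to 10 ng/mL and no more.

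**4. Sensitivity to clearance (Tac-LCP, 50 kg, ratio 2).**

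- At 120 L/h the trough is 0.69 ng/mL, 6.9-fold above 0.10.
- At 300 L/h it is 0.28 ng/mL, 2.8-fold above.
- It meets 0.10 ng/mL at 4,000,000 / 24 / (2 × 0.10) = 833,333 mL/h, or 833 L/h.

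That break-even depends on the assumed weight and ratio. At 40 kg and ratio 3 it is 3,200,000 / 24 / (3 × 0.10), about 444 L/h.

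**5. The same check in reverse.** Take 60 to 90 kg and treat the trough as the average level. The doses are then 4.8 to 9.0 mg/day. Required clearance = daily dose / 24 h / level.

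- For 0.07 to 0.10 ng/mL: from 4,800,000 / 24 / 0.10 = 2,000 L/h to 9,000,000 / 24 / 0.07 = about 5,360 L/h.
- For 7 to 10 ng/mL: 100-fold less, about 20 to 54 L/h.

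**The case against.** The best case on the other side has four parts.

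**Proof.** The documents never say ng/mL. Calling a clearance of 444 or 833 L/h implausible needs a figure from outside them. The predicted range is about 30-fold wide, and starting doses need not land on the target. This stands as a limit on certainty about the intended unit, and it is why the fix begins with a confirmation. It does not rescue the printed unit, which falls short of every prediction in the assumed range by at least about 14-fold.

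**Practical effect.** Starting doses are the center's usual ones, D2 ties the step-down to the center's own goals, nephrologists may adjust goals, and the levels are standard-of-care labs. Clinicians will probably recognize the slip. This stands, and it sets the severity. The safeguards do not correct the text, though. The discretion clause covers clinical reasons in individual patients, and E3 3.b repeats the target without it.

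**Statistical effect.** A reader might infer that the error biases the comparison or undermines the analysis. The documents do not support that. The target is the same in both arms, and no endpoint, sample size or analysis in section G uses it. The planned comparison of tacrolimus variability (C3, E3 3.e, F11) uses measured levels, not the target.

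**Size.** A reader might divide the highest prediction by the lower printed limit (41.7/0.07 = 595) and report a larger multiple. Excess over a range is measured from its upper limit, which gives 417. The missing unit on the later range is trivial by itself, since the unit carries over within the sentence.

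**Conclusion.** The point holds as a minor unit error in an operative dosing target. The 100-fold difference between the printed unit and the same numbers in ng/mL is exact. The conflict with the starting doses, about 14- to 417-fold above the printed upper limit, rests on the assumed weight, clearance and average-to-trough ratio. Its direction survives much higher clearances than those assumed. That ng/mL was meant is an inference: the doses are compatible with it, but the documents do not state it.

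Two stronger readings should be set aside. The protocol made no miscalculation, because the target is not derived from anything. Nor do the documents show that patients would be underdosed: that would follow only if the sentence were applied literally, against the center's usual practice.

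**What to change.** Confirm the laboratory's reporting unit and the goals in the center's protocol. Then change ng/dL to ng/mL in D2 and E3 3.b, and write the later target as 5 to 7 ng/mL in both places. If the laboratory does report in ng/dL, the numbers need checking instead, since 7 to 10 ng/mL would be 700 to 1,000 ng/dL. The cost is two sentences, with no change to visits, patients, data collection or analysis.
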